#### **Secondary Outcomes**

Secondary outcomes will include:

- Comparison of the relationships between LVMI/unindexed LV mass and BP indices measured by;
  - a. The HeartGuide Watch BP monitor
  - b. ABPM
  - c. Seated clinic BP
- 2. Comparison of the relationships between CAVI parameters and BP indices measured by;
  - a. The HeartGuide Watch BP monitor
  - b. ABPM
  - c. Seated clinic BP
- 3. Relationships between ECG voltage criteria for LV mass and BP indices measured by;

#### 23/37

CONFIDENTIAL - HeartGuide BP LVMI Study Protocol - Version 1.0, 09 December 2020 - EDGE 132948; IRAS 280191

- The HeartGuide Watch BP monitor
- b. ABPM
- c. Seated clinic BP
- 4. Relationship between CAVI indices and MRI parameters including;
  - a. LVMI/unindexed LV mass
  - b. Cardiac volumes
  - c. Indices of vascular structure/function
- 5. Relationships and any significant differences between various BP indices measured by:
  - a. The HeartGuide Watch BP monitor
  - b. ABPM
  - c. Seated clinic BP

All data will be analysed for distribution pattern and tested using appropriate methods. Summary statistics for continuous variables will be reported as means and standard deviation or 95% confidence intervals where appropriate. Categorical variables will be reported as n and percentage. Analysis of secondary outcomes will use similar techniques as used for the primary outcome i.e. Pearson's correlation coefficient calculated for the relationships between various BP parameters and cMRI measurements of LV mass, CAVI measurements or ECG voltage criteria for LV mass. The relationship between cMRI parameters and CAVI indices will also be determined using Pearson's correlation coefficient. Additionally, regression coefficients for all relationships will be calculated using linear regression models. Fisher's r to z transformation will be used to compare correlation coefficients between BP modes and MRI or CAVI or ECG-derived parameters. Direct comparison of BP indices will use student's t-tests, one-way ANOVA or other appropriate tests for non-normally distributed data. Data will also be plotted using Bland-Altman plots. Data may also be adjusted for potentially confounding demographic and anthropometric parameters where appropriate. A two-sided significance level of  $P \leq 0.05$  will denote statistical significance. Effect size will also be reported. Due to the relatively small sample size, it is not anticipated that any sensitivity analyses will be carried out.

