Recently a wristwatch style monitor was developed for the measurement of out of office BP (HeartGuide, Omron, Japan). This is smaller, lighter and less intrusive than conventional ABPM monitors and does not depend on an upper arm cuff. Instead, the cuff is incorporated in the strap of the watch (see fig. 2) which allows the patient to activate self-measurement of their BP multiple times during the day, either whilst seated (e.g. similar to HBPM) or when ambulant (similar to ABPM). The device prompts the user via a short vibration at the wrist, to position their wrist at heart level, immediately prior to BP measurement. In a recent study, we showed that BP measured with this device correlated very well with BP measurements using upper-arm cuff-based ABPM when BP was recorded by the HeartGuide watch immediately after each activation of ABPM BP measurement. The present study will extend these findings and evaluate whether average systolic BP measured using the HeartGuide watch is correlated with left ventricular mass index (LVMI) and a comparison of the strength of that correlation with that observed for 24-hour ABPM mean systolic BP and seated office clinic systolic BP. LVMI is the main outcome measure because hypertrophy of the left ventricle is a validated biomarker of elevated pressure and is itself potently correlated with increased risk of adverse cardiovascular outcomes and mortality. The study will use cardiac MRI (cMRI) to measure LVMI because cMRI is recognised as the most accurate and reproducible means of measuring LVMI.

In addition to the measurement of LVMI as the primary outcome, this study will also examine the relationship between different BP parameters and vascular biomarkers of hypertensive injury using the non-invasive measurement of the Cardio-Ankle Vascular Index (CAVI).

The findings of this study will provide evidence of the validity of HeartGuide watch BP measurements when compared with conventional upper arm cuff-based BP measurements and for the first time evaluate the relationship between these various BP measurement techniques and markers of hypertension-mediated organ damage, specifically LVMI. These findings will be important to help define whether the HeartGuide watch BP monitor can provide an alternative means to characterise BP levels for the diagnosis of hypertension and monitoring the response of patients to antihypertensive therapy.

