An interesting aspect of the study is that the measurement of BP with the HeartGuide watch BP monitor will be used to measure BP whilst rested and seated in the morning and evening, thereby mimicking the usual pattern of BP measurement recommended in guidelines for HBPM with a conventional upper-arm cuff-based device. However, the HeartGuide watch BP monitor also allows for BP measurements to be taken at other multiple times during the day. This is similar to the profile of BP measurements taken by ABPM but, with measurements over multiple days unlike ABPM which typically only measures BP over a single day. In this regard, the HeartGuide watch BP monitor will provide a different profile of BP measurement when compared to conventional HBPM or ABPM. It is a key additional objective of this study to define whether this new profile of BP measurement reveals any difference in the strength of the correlation between BP and LVMI.

This protocol describes the UK based study. A similar protocol will be used for a parallel study of similar size and design, developed with our collaborators at the Jichi Medical University in Japan. The plan is to evaluate the data from both studies independently but also combine the results of both studies to evaluate the relationship between BP measurement methods and indices and LVMI in different population cohorts representing Europe and Asia.

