# **Study Design**

This is a single centre cross-sectional study in 50 people with elevated systolic BP i.e.  $\geq$  130 mmHg, or receiving antihypertensive therapy. The study evaluates the relationships between BP measured with different validated and CE-marked devices, used for their intended purpose, and LVMI, measured by cMRI. The study does not involve any treatments or interventions.

A parallel study of similar design and purpose is also planned to be undertaken Jichi Medical University, Tochigi, Japan. This will allow for comparison of BP relationships with LVMI across two different population cohorts. To facilitate this two-centre analysis, non-identifiable data from both studies will be merged.

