# **Study Processes**

Each participant will be required to attend three outpatient visits for this study. The study visits can be performed on multiple days at the patient's convenience and according to their availability. Figure 1 summarises the design of the study and table 1 summarises the study visits and procedures. All study visits and procedures should ideally be performed within one month of visit 1.

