# **Statistical Analysis Plan and Data Analysis**

#### Primary Outcome analysis and Sample size estimation

The primary outcome is the association between mean "out of office" systolic BP measured by the HeartGuide watch BP monitor and LVMI measured by cMRI. This relationship will be assessed by Pearson's correlation coefficient for normally distributed data. For the primary outcome, based on 50 cases, using an estimated Pearson's correlation coefficient of 0.30, using data on the relationship between 24-hour ABPM and cMRI LVMI from our prior studies, the power would be 0.56 at P = 0.05. With 50 cases and a correlation coefficient of 0.40, the power would be 0.83 at P = 0.05. For the full analysis with 100 cases (merged analysis with the Jichi Medical University study data), at a correlation coefficient of 0.30, the power is 0.86, and a correlation coefficient of 0.40, the power is 0.99 at P = 0.05.

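### The comparison of BP–LVMI correlations between BP modes by Fisher's r-to-z makes no allowance for all modes being measured in the same participants; as usually applied, the test is conservative here

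*Protocol*

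**What the plan says.** The method is fixed in the protocol's Secondary Outcomes text: "Fisher's r to z transformation will be used to compare correlation coefficients between BP modes and MRI or CAVI or ECG-derived parameters". No standard error is given there, and dependence between the correlations is not mentioned.

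The comparison it serves is the first secondary outcome: "Comparison of the relationships between LVMI/unindexed LV mass and BP indices measured by" the watch, ABPM and seated clinic readings. Background and Purpose of the Study places it beside the primary correlation, as "a comparison of the strength of that correlation with that observed for 24-hour ABPM mean systolic BP and seated office clinic systolic BP". On the watch's multi-day measurement profile, the same section states: "It is a key additional objective of this study to define whether this new profile of BP measurement reveals any difference in the strength". The strength in question is that of the BP–LVMI association.

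The design is one cohort: "This is a single centre cross-sectional study in 50 people with elevated systolic BP" (or on antihypertensive treatment), and "Each participant will be required to attend three outpatient visits for this study". Across those visits every participant has office BP, HeartGuide, 24-hour ABPM and one MRI. A second cohort of similar size in Japan is to be merged, giving 100 cases.

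**The concern.** The correlations of HeartGuide, ABPM and office BP with LVMI all come from the same people and share the same LVMI values. They are dependent, overlapping correlations. If the BP modes correlate positively with each other, the sampling errors of the three coefficients move together, and the difference between any two varies less than it would between separate samples.

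The familiar Fisher comparison of two coefficients takes the variance of the difference as 1/(n1−3) + 1/(n2−3), which has no covariance term. Applied here it overstates the standard error. The test then rejects too rarely, and the interval for the difference is too wide. The same applies to the comparisons against CAVI and ECG measures that the sentence covers.

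At stake is the study's ability to say whether one way of measuring BP tracks LVMI better than another. The protocol also expects no sensitivity analyses, so no planned check would bring the problem to light.

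**Working it through.** **The plan's own figures.** These concern one correlation against zero, with power Φ(atanh(r)·sqrt(n−3) − 1.96):
- n = 50, r = 0.30: Φ(2.122 − 1.96) = 0.56. r = 0.40: Φ(2.904 − 1.96) = 0.83.
- n = 100, r = 0.30: Φ(3.048 − 1.96) = 0.86. r = 0.40: Φ(4.172 − 1.96) = 0.99.

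All four agree with the protocol. It gives no power for comparing two correlations.

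**Inputs.** From the protocol: n = 50 (UK) and 100 (merged), two-sided 0.05, and BP–LVMI correlations of 0.30 and 0.40. Assumed: inter-mode correlation r12 = 0.3, 0.5, 0.7 or 0.8, and alternatives of 0.20 or 0.10 for the weaker mode. The protocol states none of these.

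**Standard error as usually applied.** sqrt(2/47) = 0.206, so significance at n = 50 needs a difference in z of 1.96 × 0.206 = 0.404. If one observed correlation is 0.40 (z = 0.424), the other must be about 0.02 or lower.

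**Standard error allowing for dependence.** The Dunn–Clark covariance of the two z values, in units of 1/(n−3), is

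c = [r12(1 − r1² − r2²) − ½·r1·r2·(1 − r1² − r2² − r12²)] / [(1 − r1²)(1 − r2²)],

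and SE = sqrt(2(1 − c)/(n − 3)). For r1 = r2 = 0.30 and r12 = 0.7:
- numerator: 0.7 × 0.82 − 0.045 × 0.33 = 0.559
- denominator: 0.91² = 0.828
- c = 0.675, SE = sqrt(2 × 0.325/47) = 0.118
- 0.206/0.118 = 1.75, so the usual SE is 1.75 times too large.

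**Type I error.** With both correlations at 0.30, the usual test has true size of about 2Φ(−1.96/sqrt(1−c)). For r12 = 0.3, 0.5, 0.7 and 0.8 this is 0.023, 0.007, 0.0006 and below 0.0001. Simulation (40,000 trivariate-normal samples per setting) gives the values in the table. Dependent-correlation tests stay close to 0.05 throughout.

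**Power for 0.40 vs 0.20.** The z difference is 0.424 − 0.203 = 0.221. At r12 = 0.7 and n = 50 the true SE is 0.117. Usual test: Φ((0.221 − 0.404)/0.117) = 0.06. Dependent test: Φ(0.221/0.117 − 1.96) = 0.47.

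Results at n = 50:

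| r12 (assumed) | Type I error, usual test | Power 0.40 vs 0.20, usual | Power 0.40 vs 0.20, dependent |
|---|---|---|---|
| 0.3 | 0.02 | 0.15 | 0.23 |
| 0.5 | 0.009 | 0.11 | 0.31 |
| 0.7 | 0.001 | 0.06 | 0.47 |
| 0.8 | about 0 | 0.03 | 0.65 |

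At n = 100 and r12 = 0.7 the powers are 0.23 and 0.78. The Steiger, Meng–Rosenthal–Rubin and Williams tests agree within about one percentage point.

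**A smaller difference, 0.40 vs 0.30, at n = 50.** The dependent test has power 0.16 at r12 = 0.7 and 0.21 at 0.8. The usual test has 0.01 or less.

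**The case against.** **The sentence names a transformation, not a test.** The Steiger and Meng–Rosenthal–Rubin tests also work on the z scale, so the wording is compatible with a correct analysis, and a separate analysis plan might supply the covariance term. This stands: that the independent-sample formula will be used is an inference. But the protocol applies the method to BP modes and says nothing of dependence, and a reader following it would most likely use the two-sample formula. The wording needs completing either way.

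**The size rests on an assumed inter-mode correlation.** This also stands. The Background reports very good agreement between watch and ABPM, but for watch readings taken immediately after each ABPM reading. Here the watch is worn for 3 to 7 days and removed for sleep, while ABPM covers a later 24 hours including sleep. Office BP may correlate less. At r12 = 0 the usual test has size 0.054 and nothing is lost, hence the range.

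**Stronger readings a reader might infer.**
- That the test almost never rejects even when one mode is clearly better. For 0.40 vs 0.10 the usual test has power of about 0.20–0.33 at n = 50 and 0.64–0.74 at n = 100 over the same range of r12.
- That the results are biased towards no difference. The coefficients are not; the test is conservative and its interval too wide.
- That the test alone explains the low power. For 0.40 vs 0.30 at n = 50 the correct test is weak too.
- That the protocol plans to claim the watch is as good as ABPM from a non-significant result. It states no equivalence claim and says effect size will be reported.

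**Conclusion.** The point holds as a gap in a named method. The protocol compares dependent, overlapping correlations by Fisher's r-to-z and makes no allowance for the pairing. If the usual independent-sample standard error is used and the BP modes are positively correlated, the test is conservative. At n = 50 its size falls from about 0.02 to practically zero as the inter-mode correlation rises from 0.3 to 0.8, and between about a third and nearly all of the attainable power for 0.40 vs 0.20 is lost (0.15 of 0.23, down to 0.03 of 0.65).

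These figures assume trivariate normality, complete data in all participants, and inter-mode correlations that the protocol does not give. The primary correlation and its power statement are untouched. This should be fixed, because the comparison is a declared key additional objective. It does not threaten the study as a whole: it is a secondary analysis, and the test can be corrected from data already planned.

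**What to change.** Replace the sentence on Fisher's transformation with wording to this effect:

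- Correlations of different BP modes with the same outcome will be compared by a test for dependent overlapping correlations (Steiger, Meng–Rosenthal–Rubin or Williams), or by a bootstrap that resamples participants, in participants with all compared modes available.
- The difference in r will be reported with its 95% CI, and a non-significant difference will not be taken as evidence that the modes are equivalent.
- The independent-sample Fisher comparison will be used only between the UK and Japanese cohorts, where the samples are separate.

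The cost is a few sentences of protocol or analysis-plan wording. No new data, visits or participants are needed. The change restores the nominal type I error. It does not give adequate power for a difference as small as 0.40 vs 0.30 at n = 50, which is why the interval and the statement on equivalence belong in the text.

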#### **Secondary Outcome Measures**

- 1. Comparison of the relationships between mean BP indices measured by; (i) the HeartGuide watch BP monitor, or (ii) ABPM, or (iii) seated office BP, with LVMI by cMRI
- 2. The relationship between all BP indices as measured by all devices and the Cardio-Ankle Vascular Index (CAVI).
- 3. The relationships between CAVI indices and LVMI and corresponding cardiac and vascular indices by cMRI.
- 4. The relationships between all BP indices and ECG voltage criteria for left ventricular mass
- 5. The relationships and any significant differences between various BP indices

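### At n = 50, a non-significant r-to-z comparison of BP–LVMI correlations between modes says little about similarity; the difference needs a 95% CI from a method for dependent correlations

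*Protocol*

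**What the plan says.** **Purpose.** The Background and Purpose section expects evidence on the validity of HeartGuide against upper-arm cuff measurement. It adds that the findings will "help define whether the HeartGuide watch BP monitor can provide an alternative means to characterise BP levels for the diagnosis of hypertension" and for following response to treatment. The same section names as a key additional objective to "define whether this new profile of BP measurement reveals any difference in the strength of the correlation between BP and LVMI".

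**Outcomes.** Secondary outcome 1 compares the BP–LVMI relationships of HeartGuide, ABPM and seated office BP. Secondary outcome 5 is "The relationships and any significant differences between various BP indices".

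**Analysis.** Under Secondary Outcomes in the Statistical Analysis Plan section, the comparison of correlations is one sentence: "Fisher's r to z transformation will be used to compare correlation coefficients between BP modes and MRI or CAVI or ECG-derived parameters". The threshold follows: "A two-sided significance level of" P ≤ 0.05. BP levels are compared by t-test or ANOVA and shown in Bland-Altman plots. Regression coefficients and effect sizes are also to be reported. Confidence intervals are mentioned only for summary statistics of continuous variables, where appropriate.

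**Power.** It is given only for testing the primary correlation against zero. The planning value is "based on 50 cases, using an estimated Pearson's correlation coefficient of 0.30".

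**The concern.** The three BP modes are measured in the same people, and the question of interest is how far apart their correlations with LVMI could be. A P value from a test of no difference does not answer that. If it is above 0.05, the reader cannot tell whether the correlations are close or the study was too small to separate them. The plan as written supplies no interval to settle it and no power figure for the comparison.

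At stake is the interpretation of secondary outcome 1, the outcome closest to the stated purpose. If HeartGuide tracked LVMI half as well as ABPM, the planned comparison could well return a non-significant result. The report would then contain no planned quantity showing that a halving had not been excluded.

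**Working it through.** **Inputs from the protocol.** n = 50 (UK) and n = 100 (merged); planning correlations 0.30 and 0.40; two-sided 5%.

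**Assumed.** The correlation ρ between HeartGuide and the comparator BP mode. The documents give no value, so it is varied over 0.5, 0.7, 0.8 and 0.9. A halved correlation (0.30 vs 0.15, 0.40 vs 0.20) serves as an example of a difference that a reader would want to know about.

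**Step 1: reproduce the stated power.** Power ≈ Φ(atanh(r)·√(n−3) − 1.96). For r = 0.30 and n = 50: 0.3095 × √47 = 2.122, and Φ(0.162) = 0.564. The protocol says "the power would be 0.56 at P = 0.05". The other three cases give 0.828, 0.862 and 0.987 against the stated 0.83, 0.86 and 0.99. All four agree.

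**Step 2: r-to-z in its usual independent form, n = 50.** SE = √(2/47) = 0.2063. For 0.30 vs 0.15 the difference in z is 0.3095 − 0.1511 = 0.1584, a ratio of 0.768, so power is 12%. For 0.40 vs 0.20 the difference is 0.2209, a ratio of 1.071, so power is 19%. These figures would hold if the two correlations came from different people. Here they come from the same people, the SE is too large, and simulated power falls further.

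**Step 3: test for dependent correlations sharing LVMI.** With a and b the two correlations, SE = √((2 − 2c)/(n−3)), where

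c = [ρ(1−a²−b²) − ½ab(1−a²−b²−ρ²)] / [(1−a²)(1−b²)].

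For a = 0.30, b = 0.15, ρ = 0.7: c = (0.62125 − 0.00894)/0.88953 = 0.688 and SE = √(0.6233/47) = 0.115. The ratio is 0.1584/0.115 = 1.375, so power is about 28% and the miss rate 72%. Simulation with the Williams test gives the values below; the formula agrees within about 4 percentage points.

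| Chance that a halving is missed, n = 50 | ρ = 0.5 | 0.7 | 0.8 | 0.9 |
|---|---|---|---|---|
| 0.30 vs 0.15, dependent test | 81% | 72% | 60% | 31% |
| 0.40 vs 0.20, dependent test | 68% | 52% | 34% | 6% |
| 0.30 vs 0.15, independent r-to-z on paired data | 95% | 98% | 99% | >99% |
| 0.40 vs 0.20, independent r-to-z on paired data | 89% | 94% | 97% | 99% |

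The lowest value for the independent form is 88.6%. By the formula, the dependent test detects the halving more often than not only once ρ exceeds about 0.86 (0.30 vs 0.15) or 0.73 (0.40 vs 0.20). At n = 100 the dependent test misses 66/49/31/6% and 44/22/7/<1%.

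**Step 4: what an interval would show.** With equal true correlations, the 95% half-width in r is about 1.96 × SE × (1−r²). At n = 50 this is 0.27/0.21/0.17/0.12 for r = 0.30 and 0.26/0.20/0.16/0.12 for r = 0.40, over the same values of ρ. At n = 100 the range is about 0.08 to 0.19.

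**The case against.** A reader might infer that the protocol plans to treat a non-significant difference as equivalence. The documents do not support that. Nowhere do they say so; the sentence about an alternative means is soft (findings will help define it) and names no equivalence hypothesis; and the stated objectives ask about differences, which a two-sided test addresses. A non-inferiority margin is therefore not something the protocol was bound to contain.

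It would also be wrong to say that modes are compared by significance tests alone. Bland-Altman plots, regression coefficients and effect sizes are planned, although no interval for the difference in correlations is specified and the plots carry no limit.

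Nor does a small sample simply favour the device. If support for HeartGuide required a significant HeartGuide–LVMI correlation as well as a non-significant difference, a halved correlation would pass both at n = 50 in only 3% to 26% of studies with a dependent test, and in about 18% to 29% with the independent form.

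Finally, the miss rate depends on ρ. The Background reports that HeartGuide and ABPM correlated very well, which points to high ρ and fewer misses. But those readings were taken one immediately after the other. Here ABPM is fitted only when the watch is returned at visit 2, and the watch is removed for sleep while ABPM covers it, so a lower value is plausible.

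All of these limit the point. None supplies the missing interval. A separate analysis plan may add detail, but the protocol itself already fixes the test and the threshold.

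**Conclusion.** The point holds as a weakness of method in a secondary analysis. The planned comparison yields a P value that, when non-significant at n = 50, is weak evidence of similarity. Over the assumed ρ of 0.5 to 0.9, a halved correlation is missed 31% to 81% of the time (0.30 vs 0.15) or 6% to 68% (0.40 vs 0.20) with a suitable test. With r-to-z in the independent form it is missed 88% or more. The protocol does not say which form it means.

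The figures assume normal data, no missing readings and the stated ρ values. At high ρ with a dependent test the UK study would usually detect a halving, so a blanket statement that it usually misses one is not justified. The primary analysis and its power figures are unaffected.

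**What to change.** In the Secondary Outcomes analysis text:

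1. Report r(ABPM, LVMI) − r(HeartGuide, LVMI), and the same difference against clinic BP, each with a 95% CI from a dependent-correlation method or a bootstrap that resamples participants. Do this for the UK data and for the merged n = 100.
2. Base any statement of comparability on that interval and on the Bland-Altman bias and limits of agreement with their CIs.
3. Add one sentence: P > 0.05 for a between-mode difference will not be interpreted as equivalence.

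A formal margin is optional and for the sponsor to choose. A strict one would be hard to meet. As an illustration, if the margin were a halving of r = 0.30 and the true correlations were equal, power at n = 50 (one-sided 2.5%) would be 18/27/38/64% over the same ρ values.

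The cost is wording and a few lines of code, with no new data or participants. The drawback is that, with a half-width of about 0.12 to 0.27 in r, the UK-only comparison will often be reported as inconclusive.
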